COVER PAGE

Official Title of the Study

Intrapartum epidural catheter displacement: Comparison of three dressing methods in morbidly obese parturients

NCT Number

NCT03574441

Protocol Title: *Intrapartum epidural catheter displacement: Comparison of three dressing methods in morbidly obese parturients*

Principal Investigator: *[name] MD*

1. Objectives

Purpose, specific aims, and hypothesis:

Purpose: We propose this study to prospectively evaluate the efficacy of the three types of epidural catheter dressings that we currently use in our Labor and Delivery unit, in terms of catheter migration, taking into consideration the influence of body mass index on this variable.

Primary aim: We will evaluate the efficacy of three different epidural catheter dressing systems in laboring patients.

Secondary aims: To compare the effect of different degrees of obesity measured by BMI, on epidural catheter migration and quality and failure of epidural labor analgesia. To evaluate the effect of time an indwelling catheter remains in place, level of insertion and patient's height on epidural catheter migration.

Hypothesis: The use of dressing with transparent TegadermTM plus SorbaView SHIELD® dressing is superior to the dressing with TegadermTM plus Steri-StripTM bands in addition to a catheter support pad, and to a dressing with TegadermTM only, for epidural catheter fixation in laboring obese and morbidly obese patients, in terms of catheter migration, epidural quality and failure and epidural catheter replacement in the labor analgesia setting.

2. Background

Background and rationale for the study:

Failure of labor epidural is a well-recognized situation in obstetric anesthesia practice. Incidence of epidural failure was shown to be 12% in a retrospective analysis of 19.259 deliveries (1). Epidural migration has been documented in both the obstetric and non-obstetric settings (2,3). It has been argued that prevention of epidural displacement is a potential remedy to at least part of the incomplete or failed epidurals in obstetrics (4,5). Motamed et al showed that 45% of epidural failures in major abdominal surgery could be attributable to catheter migration (6). Phillips et al studied epidural catheter migration in labor finding an incidence of 54% (7). Migration was 2 cm on average and tended to be directed inward. Crosby et al found a similar incidence of catheter migration but in an outward direction (8).

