Factors influencing catheter migration include weight, body mass index, depth of the epidural space and patient positioning (9,10). Bishton et al documented inward migration in 13% and outward displacement of one or more centimeters in 22% of patients in a cohort of 153 laboring patients (10). They also found that all cases of failed epidural occurred in patients with outward migration greater than 2,5 cm (10). Hamilton et al showed an association between patient position change and movement of epidural catheters, when the patient is sitting with a straight back and when placed on lateral decubitus position (11). The authors found that the magnitude of epidural catheter movement was more pronounced in patients with $BMI > 30 \text{ kg/m}^2$. It has been hypothesized that the epidural catheter might be fixed to the ligamentum flavum after it is threaded, as the maximum pressure found during catheter placement corresponds to this anatomical structure (12). When the patient changes position after taping the catheter, especially in the case of a parturient with high BMI, the new anchor point theoretically moves to the skin, facilitating outward migration of the epidural catheter (9).

Some authors have evaluated the influence of different dressing methods on epidural catheter migration. Burns et al compared Tegaderm™ dressing, Tegaderm™ plus filter-shoulder fixation and Niko Epi-Fix dressing in 113 patients in labor (2), finding that Tegaderm™ plus filter-shoulder was superior in terms of minimization of epidural catheter displacement. Their study doesn't mention weight or BMI of patients included in the study. Odor et al evaluated the efficacy of Epi-Fix™, Lockit Plus® and Tegaderm™ for dressing of intrapartum catheters, finding superiority of the Lockit Plus® system to decrease catheter migration and epidural analgesic failure (13). The authors didn't evaluate the effect of BMI on the outcomes and even excluded patients with $BMI > 50 \text{ kg/m}^2$. Similar results were reported by Clark et al in a cohort of 102 patients having epidural catheters for major non-obstetric procedures (14).

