d. Duration of an individual subject's participation in the study and the time involved:

The patients will be participating in the study for as long as the epidural catheter remains in place for clinical indications. The expected time will be between 6 and 12 hours.

7. Data and Specimen Management

a. Data analysis plan:

Sample size: Based on previous experiences for a measurable difference of 0,5 cm, we will include 35 patients in each group to have a power of 90% and a statistical significance level of 0,05. Data will be analyzed using analysis of variance, Student's t test, chi-square test and Pearson's correlation coefficients where appropriate.

N/A

b. Power analysis:

See above

N/A

c. Data handling:

N/A

i. Information included in the data

Following dressing application, demographic variables of each patient will be recorded including (age, gravity, parity, weeks of gestation, weight, height, BMI). Other recorded variables include time of insertion, distance from catheter tip to skin in centimeters. One hour after delivery, immediately before catheter removal, time, duration of catheter presence, centimeters from skin to catheter tip and dressing integrity will be recorded. Dermatomal level and symmetry of the block will be recorded every two hours or every time the patients requires a top-up dose. We will also record number of top up doses and rate of epidural infusion as well as the need for catheter replacement during the observation period.

Primary outcomes

Epidural catheter migration (ECM) in centimeters = Distance from tip to skin at insertion - Distance from tip to skin at removal. If the catheter moves inward, ECM will be negative and if it gets displaced outwardly, ECM will be positive.

Secondary outcomes

- 1) Dermatomal sensory level measured with thermal discrimination
- 2) Incidence of asymmetric block
- 3) Rate of epidural catheter replacement
- 4) Total epidural dose (mL)
- 5) Number of top-up epidural boluses.

ii. Data storage

Data derived from the study will be stored in a locked drawer in the office of the PI for the duration of the study. The de-identified information will be accessed by the research team and the statistician for analysis.

iii. Duration of data storage

For one year after study completion.

iv. Access to data

The PI and the research team.

v. Responsible for receipt or transmission of the data

The Principal Investigator

vi. Data transport

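### The only primary outcome is signed catheter migration, so a comparison of arm means lets inward and outward moves offset and can miss a dressing that reduces movement

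*Combined protocol and SAP*

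**What the plan says.** - **Hypothesis (section 1).** One dressing is expected to be superior "for epidural catheter fixation in laboring obese and morbidly obese patients, in terms of catheter migration", among other measures.
- **Primary outcome (section 7c.i).** ECM is the tip-to-skin distance at insertion minus the same distance at removal, in cm. The sign is kept: "If the catheter moves inward, ECM will be negative and if it gets displaced outwardly, ECM will be positive". It is the only primary outcome. The five secondary outcomes cover sensory level, asymmetric block, catheter replacement, total dose and top-ups; none measures movement. Section 9b mentions an incidence of migration as a ground for stopping, but it is not defined and is not an outcome.
- **Analysis (section 7a).** "Data will be analyzed using analysis of variance, Student's t test, chi-square test and Pearson's correlation coefficients where appropriate". No test is tied to ECM.
- **Sample size (sections 4 and 7a).** "for a measurable difference of 0,5 cm, we will include 35 patients in each group to have a power of 90" per cent, at the 0.05 level. The plan gives no SD and does not say whether the 0.5 cm is signed or absolute.
- **Direction of movement (section 2).** One labor study is cited for "epidural catheter migration in labor finding an incidence of 54" per cent, and "Migration was 2 cm on average and tended to be directed inward". A second "found a similar incidence of catheter migration but in an outward direction". A third, of 153 laboring women, had "inward migration in 13% and outward displacement of one or more centimeters in 22% of patients", and all its failed epidurals were in women whose catheters had moved outward by more than 2.5 cm. The Background theorises outward movement at high BMI, and says that migration has not been studied in a high-BMI obstetric population.

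**The concern.** Better fixation means that the catheter moves less. The mean of a signed distance measures something else, the net drift of an arm: a patient whose catheter goes in 2 cm cancels one whose catheter comes out 2 cm. An arm in which many catheters move both ways can have the same mean as an arm in which none move.

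If this population moves in both directions, the primary comparison could find no difference between dressings that do differ in how well they hold the catheter. Both distances are recorded, so |ECM| could be derived later. But a switch made after the data are seen would be post hoc, and section 8f has the cumulative data reviewed every week.

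**Working it through.** **1. The plan's own figure.** From the plan: 35 per group, difference 0.5 cm, power 90%, level 0.05. Without an SD the 35 cannot be reproduced, only inverted. For a two-sided pairwise t test at n = 35 the detectable standardised difference is 0.786, so the implied SD is 0.5 / 0.786 = 0.636 cm. Other readings give 0.71 cm (one-sided), 0.57 cm (Bonferroni for three pairs) and 0.58 to 0.67 cm (three-group ANOVA, depending on the middle mean). None of this shows which scale was meant.

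**2. The cancellation.** Let a fraction p_out move outward and p_in inward, each by m cm. Without noise:

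- mean signed ECM = m × (p_out − p_in)
- mean |ECM| = m × (p_out + p_in)

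With 22% and 13% from section 2 and an assumed m = 2 cm, these are 2 × 0.09 = 0.18 cm and 2 × 0.35 = 0.70 cm. Assumed reading noise with SD 0.2 cm gives non-movers a mean |ECM| of 0.2 × √(2/π) = 0.16 cm, so the absolute mean becomes 0.70 + 0.65 × 0.16 = 0.80 cm. The effect of a dressing is then:

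- All movement stopped: the signed mean changes by 0.18 cm, the absolute mean by 0.80 − 0.16 = 0.64 cm.
- Outward moves only stopped: the signed mean goes from 0.18 to −0.26 cm, a change of 0.44 cm. The absolute mean falls by 0.22 × (2 − 0.16) = 0.40 cm.
- Inward moves only stopped: the signed mean rises from 0.18 to 0.44 cm while the absolute mean falls from 0.80 to 0.56 cm. The dressing that holds better then has the larger signed mean.

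**3. Power.** This was simulated: 20,000 trials per case, 35 per arm, two-sided 0.05, 0.2 cm noise, Student t on signed ECM and Welch t on |ECM|. The type I error was about 5% on both scales. Entries are signed versus absolute, reproducible to about 1 point.

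| Control arm | Effect of the better dressing | All such moves stopped | 75% fewer |
|---|---|---|---|
| 22% out, 13% in, 2 cm | both directions equally | 14% vs >99% | 9% vs 78% |
| 22% out, 13% in, 2 cm | outward only | 46% vs 57% | 26% vs 34% |
| 54% move 2 cm, 80/20 outward | both directions equally | 78% vs about 100% | 47% vs 96% |
| 54% move 2 cm, 80/20 outward | outward only | 92% vs 98% | 63% vs 81% |
| 35% move 1.5 cm, all outward | outward | 99% vs >99% | 74% vs 76% |

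The 22%, 13% and 54% come from section 2. The 2 cm is an average that section 2 gives for the 54% study only; the 80/20 split, the 1.5 cm and the noise are assumed. With 50% fewer moves, the 22/13 mix gives 6% vs 38% (both directions) and 13% vs 16% (outward only); the all-outward case gives 35% vs 36%.

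**4. Sensitivity.**

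- With 0.5 cm noise and both directions reduced, the 22/13 mix gives 12% vs 97% (all stopped) and 9% vs 67% (75% fewer). The all-outward case gives 87% vs 91% and 55% vs 57%.
- The 1 cm threshold in section 2 may apply to the outward figure only, so smaller outward moves may be uncounted. Adding 20% with 0.5 cm outward moves and setting inward moves to 1 cm (both assumed) gives 69% vs about 100% and 37% vs 84%.

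**The case against.** Four points have weight.

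**Direction matters clinically, and may be mostly outward here.** Section 2 ties failed epidurals to outward movement and theorises outward movement at high BMI. If all movement is outward, the signed mean loses almost nothing. This stands as a limit on the size of the problem. It does not rescue the signed mean as a measure of outward movement, because any inward moves in other patients are still subtracted.

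**The largest gaps assume that a dressing cuts both directions by the same fraction.** The documents do not say that it does. If only outward moves are prevented, the signed test is weaker by about 11 points in the 22/13 case and 6 in the 80/20 case with all outward moves stopped. This stands.

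**|ECM| has its own blind spot.** If one arm has 43% out and 11% in and another has the reverse, at 2 cm each, signed power is 97% and |ECM| power about 5%. This stands, and is why signed ECM must remain a prespecified outcome.

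**Part of the shortfall is spread, not cancellation.** The simulated control-arm SD of signed ECM is 1.19 cm (22/13) and 1.33 cm (80/20), about twice the 0.64 cm that the design implies. This stands too, and is a reason to state the SD.

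A reader might infer that the trial has only about 14% power, or that signed ECM should be dropped. The documents support neither. The first rests on assumed distances, an assumed effect pattern and a direction mix from a different population. The second ignores the link to failure in section 2. Nor does the plan state that mean signed ECM will be tested. That is inferred from the cm scale, the 0.5 cm difference and the listed ANOVA and t tests.

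**Conclusion.** The point holds in conditional form. If arm means of ECM are compared and catheters move both ways, the primary test measures net drift and can miss a dressing that reduces movement. That follows from arithmetic and needs no assumed distances.

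The practical size is uncertain. For a mix near 22/13 the loss is large if the dressing reduces both directions alike and modest if it prevents outward moves only. It is negligible if all movement is outward. In none of the movement-reducing cases tabulated was |ECM| less powerful than signed ECM. Confidence is high on the mechanism and moderate on the impact. It should be fixed before outcome data are examined.

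**What to change.** - **Section 7c.i.** Define the primary outcome as |ECM|, the absolute difference between the two tip-to-skin distances in cm, because this matches the fixation hypothesis. Keep signed ECM, and the proportion with outward migration above 2.5 cm, as prespecified secondary outcomes.
- **Section 7a.** State that mean |ECM| is compared across the three dressings with the ANOVA and t tests already listed, in a form that allows unequal variances (Welch).
- **Sections 4 and 7a.** State which scale the 0.5 cm refers to, the assumed SD on that scale, and the resulting power at 35 per group, even if it is below 90%.

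The cost is a few sentences and no new data. The downsides are that inward and outward moves count equally in the primary outcome, that direction becomes secondary, and that the restated power may be lower. Two examples with 0.2 cm noise:

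- 35% moving 2 cm and 75% fewer moves: a drop in mean |ECM| of 0.35 × 0.75 × 1.84 = 0.48 cm, with about 77% power.
- 54% moving 2 cm and 50% fewer moves: a drop of 0.54 × 0.50 × 1.84 = 0.50 cm, with about 63% power.

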- a. *Procedures involved to include those procedures that are standard evaluation and/or care and those that are solely for research purposes:*

After approval by the Institutional Review Board, we will obtain consent from the participant patients. Patients will be randomized using a random number table to be allocated to one of three groups with sealed envelopes, based on the type of dressing to be used to secure the epidural catheter after its insertion:

- 1) Tegaderm™ plus SorbaView SHIELD® dressing
- 2) Dressing with Tegaderm™ plus Steri-Strip™ bands in addition to a catheter support pad (All included in the epidural kit)
- 3) dressing with Tegaderm™ only

Patients will have an epidural catheter placed for labor. We will use the standard epidural kit (Smiths Medical ASD Inc. Keene, NH. USA). The technique will consist of the use of a 17G Tuohy needle using a midline

approach with the patient in the sitting position. Localization of the epidural space will take place using loss of resistance to air or saline per anesthesiologist's preference. A 20G epidural catheter will be inserted to leave 5 cm into the epidural space (distal to the tip of the Tuohy needle). After the Tuohy needle is removed and the catheter is considered to be at an adequate depth, the patients will be asked to sit up straight. Then, a test dose with 3 mL of Lidocaine 1,5% with epinephrine 1:200.000 will be injected through the catheter into the epidural space, and a dressing varying depending on the assigned group will be applied. The rest of the catheter will be secured longitudinally along the patient's back over the shoulder.

b. Study design:

This is a randomized controlled clinical trial.

c. Procedures performed to lessen the probability or magnitude of risks:

The application of the three types of epidural dressings analyzed in this study are part of our current standard clinical practice. There is no additional risk due to our intervention. We will protect the rights of the patient maintaining confidentiality (records will be de-identified and assigned a study number) and patients can revoke their consent to participate at any moment during the study. Visual evaluation of the site of insertion of the epidural catheter will be inspected during the study period and any signs of topical or allergic reactions to any of the components used for dressing will be identified and treated accordingly should it happen.

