From the site of data collection to the PI office by the Principal Investigator.

8. Provisions to Monitor the Data to Ensure the Safety of Subjects

a. Data safety and delivery plan

The Principal Investigator (PI) will be responsible for the conduct of this study, including overseeing participant confidentiality, executing the Data and safety Monitoring (DSM) plan, and complying with all reporting requirements to local and federal authorities. This oversight will be accomplished through additional oversight from a Data and Safety Monitoring Committee at the Augusta University. We will conduct ongoing review of all serious adverse events (SAEs), unanticipated problems (UAPs) and reportable adverse events (AEs). Per the DSM Plan, SAEs, UAPs and reportable AEs will be reported to the institutional committee and IRB per study protocol. All SAEs, UAPs and reportable AEs are to be reported to the committee and IRB within 5 business days of receiving notification of the occurrence.

Audits will consist of a review of the regulatory documents, consent forms, and source data verification. Results and recommendations from audits will then need to be submitted by the PI to the IRB of record at the time of the continuing review.

b. Data review.

We will review the results for analysis at the end of data collection. The participants will be informed from the beginning of the study that any concerns related to the study be communicated directly to the PI, who will address them according to the DSM plan.

c. Collection of safety information

Data will be de-identified right after collection and be kept as paper record in the PI office.

d. Frequency of data collection

Data will be collected daily.

e. Responsible of data review.

The research team (PI and 2 co-investigators) will collect and analyze data.

f. Frequency of data review

Every week there will be a review of the cumulative data.

g. Conditions that trigger an immediate suspension of the research.

N/A

9. Withdrawal of Subjects

N/A

a. Anticipated circumstances under which subjects will be withdrawn from the research without their consent.

Patients will be withdrawn from the study if she develops an allergic or topical reaction to dressing or if the dressing has to be replaced due to soiling or bleeding.

N/A

b. Procedures for orderly termination.

N/A

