If during the preliminary data review one of the dressings is performing significantly better or worse than the others, or if one of the groups has higher incidence of catheter migration than that reported in the literature, the study will be terminated and the results analyzed up to that point.

c. Procedures that will be followed when subjects withdraw from the research

N/A

If there is withdrawal of consent or if a subject is withdrawn without consent for the circumstances cited above, those cases will be included in the analysis as "lost to follow-up" and reported in the results section.

10. Risks to Subjects

a. *Foreseeable risks.*

No risks additional to standard clinical care are foreseen. Topical or allergic reactions to the dressing materials would be managed by removal of the dressing and topical treatments.

b. *Costs that subjects may be responsible for because of participation in the research.*

N/A

N/A

c. *Risks to others who are not subjects.*

N/A

N/A

11. Potential Benefits to Subjects

There is no direct benefit to patients expected from their participation in this study. It is hoped the knowledge gained will be of benefit to other patients in the future.

12. Confidentiality

Procedures for maintenance of confidentiality.

See above

13. Consent Process

Before enrollment in the study, patients will be explained the purposes of the study, the risks and the procedures that will take place as part of the study. Time will be given to answer questions and PI contact information will be provided. Then, the patient will be given the opportunity to decide about participation in the study by signing the consent. The possibility of revoking the consent at any time during the study will also be explained (See consent form for details)..

14. Compensation for Research-Related Injury

This section is not required when research involves no more than Minimal Risk to subjects. **N/A**

a. *Describe the available compensation in the event of research related injury.*

N/A

15. Resources Available

N/A

a. *Availability of medical or psychological resources that subjects might need as a result of an anticipated consequences of the human research.*

N/A

b. *Process to ensure that all persons assisting with the research are adequately informed about the protocol, the research procedures, and their duties and functions.*

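### Sections 9a and 9c remove randomised patients from the primary outcome for dressing events that may depend on the arm, and no reading is scheduled for a catheter replaced in labour

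*Combined protocol and SAP*

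**What the plan says.** - **Allocation.** Section 6a: "Patients will be randomized using a random number table", to one of three dressings. All three include Tegaderm; two add further components.
- **Withdrawal.** Section 9a withdraws, without her consent, a patient who "develops an allergic or topical reaction to dressing or if the dressing has to be replaced due to soiling or bleeding".
- **Handling.** Section 9c covers these patients: "if a subject is withdrawn without consent for the circumstances cited above, those cases will be included in the analysis as" a named category. That category is lost to follow-up. The cases are to be reported, but no ECM reading or value is stated for them. Section 7a lists ANOVA, t test, chi-square and Pearson correlation, with no analysis set and no rule for missing data.
- **Primary outcome.** Section 7c.i defines ECM as "Distance from tip to skin at insertion - Distance from tip to skin at removal". The final reading is scheduled once: "One hour after delivery, immediately before catheter removal, time, duration of catheter presence, centimeters from skin to catheter tip" are recorded then.
- **Catheter replacement.** It is not a reason for withdrawal. Section 7c.i records the need for it, and its rate is secondary outcome 3. Section 1 hypothesises superiority of one dressing "in terms of catheter migration, epidural quality and failure and epidural catheter replacement in the labor analgesia setting". Section 6d has patients take part "for as long as the epidural catheter remains in place for clinical indications", without saying whether a second catheter continues participation.
- **Mitigating text.** Exclusion 1 in Section 3 removes patients with a known allergy to adhesive tape or to the dressing components.

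**The concern.** A skin reaction, or a dressing changed for soiling or bleeding, happens after randomisation and happens to the assigned dressing. If these events are more common in one arm, and the patients affected migrate more or less than the rest, dropping them leaves arms that are no longer comparable on the primary outcome. They are also not lost in the usual sense. Section 10a manages reactions by removing the dressing, so staff are at the insertion site, and a catheter that stays in can still be read at its own removal.

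The replaced catheter is a separate gap. Section 2 cites a cohort in which every failed epidural had outward migration above 2.5 cm. If a catheter replaced in labour is not read when it comes out, some of the largest migrations may go unrecorded. If ECM is then taken from the second catheter, it describes a different catheter with a shorter dwell time.

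**Working it through.** **1. The plan's own figure.** Section 7a gives 35 per group for a 0.5 cm difference, 90% power and a 0.05 level. It states no SD, so 35 cannot be reproduced independently; only the SD can be back-solved. With a two-sided, two-arm t test (noncentral t), 90% power at n = 35 per arm needs a standardised difference of 0.786, so SD = 0.5 / 0.786 = 0.636 cm. Other conventions (normal approximation, one-sided, alpha divided by 2 or 3, three-arm ANOVA) give 0.569 to 0.715 cm. The plan states no allowance for losses.

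**2. Bias from loss in one arm (assumed, not from the documents).** Let ECM be normal and let a fraction q of one arm, its most extreme readings on one side, be missing. With φ the standard normal density and z the quantile at 1 − q:

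- shift in that arm's mean = SD × φ(z) / (1 − q)
- q = 0.10: φ(1.282) / 0.90 = 0.1755 / 0.90 = 0.195; 0.195 × 0.636 = 0.124 cm
- 0.124 / 0.5 = 25% of the target difference
- over SD 0.569 to 0.715 cm: 0.11 to 0.14 cm, or 22% to 28%

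The direction is open. Losing the most outward readings from the worse arm shrinks the difference; losing them from the better arm widens it. Ten per cent of 35 is 3.5 patients.

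**3. Unequal loss in two arms.** With 5% missing in one arm and 15% in another, the multipliers are 0.109 and 0.274. The shifts are 0.069 and 0.174 cm, and the net effect is 0.105 cm (21%).

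**4. Equal loss.** The same fraction lost in the same way from every arm shifts each mean equally, so the difference is unbiased in this model. The cost is power. For losses unrelated to ECM, 10%, 20% and 30% leave 31, 28 and 24 per arm (rounded down), and power falls from 90% to 86%, 82% and 76% at SD 0.636 cm.

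**5. Replaced catheters.** Set side by side, the ECM formula refers to removal, which can cover a catheter taken out early. The schedule gives one time, an hour after delivery, when a catheter replaced in labour is no longer in place. No section says which catheter supplies ECM. For scale, Section 2 reports: "Incidence of epidural failure was shown to be 12% in a retrospective analysis of 19.259 deliveries". Applied to one arm, 0.12 × 35 = 4.2 patients. That is failure, not replacement, and the documents give no replacement rate, so no size is claimed for this part.

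**The case against.** The strongest reply is that the documents contain no evidence of arm-related loss. Known allergies are excluded at entry, Tegaderm is in every arm so only the added components differ, and expected exposure is 6 to 12 hours. Nothing links soiling or bleeding to a dressing type. All of this stands. It limits the allergy part and makes the dependence on arm a possibility rather than a finding. It does not justify a rule that discards the outcome when the event occurs.

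A second reply is that the formula says removal, so the natural reading is the first catheter, measured whenever it comes out. That is reasonable, and it means the replacement gap is closed by one clarifying sentence. A reader might infer that replaced catheters have no ECM by definition; the formula does not support that. What is missing is the scheduled reading and the choice of catheter.

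A third is that Section 9c says these cases are included in the analysis. They are included under a label, and a patient without an ECM value cannot enter an ANOVA or t test of ECM.

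A reader might also infer a much larger bias, for example 0.20 cm (40% of target) from a 10-point excess loss of patients who differ by 2 cm from those kept. That does not fit the plan's implied spread. Two centimetres is 2 / 0.636 = 3.1 SDs, and a 10% subgroup that far away would alone contribute 0.1 × 0.9 × 2² = 0.36 of a total variance of 0.636² = 0.404. For normal ECM, the gap when exactly the extreme 10% are lost is about 1.24 cm.

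**Conclusion.** The point holds as a defect in the stated rule. Following Sections 9a and 9c as written drops primary-outcome data after randomisation for events that may depend on the assigned dressing. It should be fixed. Confidence is high for the reading of the text, not for the presence of bias, whose direction and size cannot be derived from the documents. The shift of about 0.12 cm (25% of the 0.5 cm target) is an illustration that rests on normal ECM, an SD of about 0.64 cm that the plan does not state, and loss of the extreme 10% in one arm only.

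The replaced-catheter gap is a separate and smaller matter: an unscheduled reading and an unnamed catheter. Such readings may be informative because of the cited link between failed epidurals and outward migration.

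A reader might extend the charge of bias to exclusion 3 (cesarean during the study period), which will often be known only after randomisation. No text links cesarean to the dressing, so the documents support only reporting these cases by arm.

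**What to change.** 1. In Sections 9a and 9c, stop treating a dressing reaction or dressing replacement as withdrawal from outcome assessment, with clinical care unchanged. Keep measuring these patients, analyse them in their assigned arm, and report the events by arm.
2. In Section 7c.i, keep the present ECM as primary and state that it is taken on the first catheter, read immediately before that catheter is removed for any reason, including replacement in labour.
3. Where the dressing is changed and the catheter stays in, also read the catheter mark at the change, and use that reading in a sensitivity analysis.
4. Report early removals, missing readings and their reasons by arm, and report cesareans after randomisation by arm.

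The cost is protocol wording, an ethics amendment for the changed withdrawal terms, and one extra mark reading when staff are already handling the dressing or catheter. There are two downsides. ECM after a dressing change partly reflects the second dressing, and a replaced catheter has a shorter dwell time. The sensitivity analysis shows how much the first matters; the by-arm reporting makes the second visible but does not remove it.
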